Pain initiates a stress response that increases sympathetic output and facilitates autonomic imbalance. Heart rate variability (HRV) is a valid, quantitative, noninvasive measure of autonomic function. HRV biofeedback (HRV-B) is a novel biobehavioral procedure whereby patients learn to restore autonomic imbalance by developing 'HRV coherence'. Patients in this state have improved mood, cognition, and executive function, and HRV-B interventions have been used to treat: pain, anxiety, depression, insomnia and symptoms of posttraumatic stress disorder (PTSD) and heart disease. We have found that HRV-B training among Veteran PTSD patients can enhance HRV coherence and improve cognition and sleep relative to controls. Importantly, our pilot study showed that HRV-B can alleviate chronic pain and stress among Veteran Pain Clinic patients. HRV-B thus has a pivotal role in restoring autonomic balance and managing pain and the symptoms that amplify it. The proposed project is a randomized, sham-controlled, biobehavioral intervention that will test the hypotheses that HRV-B increases HRV coherence and reduces pain, stress, fatigue, insomnia and depression and improves sleep, activity, and cognition. Because this is a behavioral intervention, it is difficult to blind the subjects to the active vs sham treatment, and the biofeedback coach who provides the training must know the condition to which the subject is assigned. However, all others in the study are blinded to the training. The specific aims are: 1.) Determine whether HRV-B increases HRV coherence and reduces pain or stress relative to a sham treatment among Veterans with chronic, nonmalignant, axial neuromusculoskeletal pain; 2.) Determine as an exploratory aim whether HRV-B reduces insomnia, fatigue or depressive symptoms, and increases sleep and activity and improves cognition among patients relative to sham treatment. We hypothesize that HRV-B will (1) reduce self-reported pain and stress ratings, (2) improve objective measures of actigraphic sleep parameters (sleep latency, duration, efficiency, fragmentation), rest/activity rhythms (dichotomy index, interdaily stability) and cognitive function (reaction time, attention); and (3) alleviate self-reported fatigue and depression symptoms. Patients from both groups will be randomized to our previously established HRV-B or sham protocol (n=40 each), and will complete a baseline assessment, 6 weekly training sessions, a post-training assessment, a 4-week booster training and assessment, and an 8-week post-training follow-up evaluation, for a total of 10 visits to the research site. Portable, hand-held, data-logging devices will be used to practice attaining HRV coherence at home by the active treatment group, while those in the sham training group will get a 'stress squeeze ball'. Standard methods will quantify HRV coherence and other HRV measures, and validated instruments will be used to assess pain and stress. Wrist actigraphy is a valid, quantitative, and noninvasive procedure that will be used to characterize insomnia via continuous recordings collected 24-hrs/day over three 1-week periods (at the baseline, post-treatment, and 8-week follow-up assessment). A small battery of tests measuring attention and reaction time will assess changes in cognitive performance. Data analyses will apply linear models for repeated measures to evaluate the effect of HRV-B on study outcomes, and on treatment persistence, after adjusting for confounding factors. For each measure we will calculate three estimates of change for each patient (post-training minus pre-training, 4-week booster minus post-training, and 8-week follow-up minus the 4-week booster assessment). Path analyses will examine direct and indirect relationships between HRV-B, the primary and exploratory outcomes, and personal or social factors that may modify these relationships. This study will be the first to examine HRV-B for pain management among Veteran chronic pain patients. This study is directly responsive to a national VHA/DoD Task Force's recommendations to provide complementary, integrative therapies for pain management to Veterans.

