Our proposal is designed to test whether HRV-B is feasible and effective in increasing HRV coherence and reducing perceived pain, stress, depression, and insomnia among Veterans suffering from chronic physical pain. Our path analyses will examine both direct and indirect relationships between HRV-B, the primary and exploratory outcomes, and other individual or social factors that may modify this relationship. The relationship

between autonomic dysfunction and disrupted sleep has not been thoroughly examined. Our path analyses are thus important from a practical standpoint because HRV coherence and sleep represent potentially modifiable risk factors that can be targeted to reduce symptom burdens and improve QoL for Veteran patients. In addition, we will implement the use of portable, hand held finger plethysmographs (personal stress relievers) to reinforce the HRV-B training and promote practice outside the clinic. We have obtained encouraging preliminary results by incorporating this technique in our other research. In our path analysis, we will identify factors predicting persistent HRV-B effects at the 8-week post-treatment follow-up. This information will be useful in designing future interventions. The use of HRV-B to normalize autonomic function represents a novel, complementary strategy that engages patients in their own care and is directly responsive to the VHA/DoD Pain Management Task Force’s recommendations to adopt complementary pain management strategies (including HRV-B) to alleviate pain among Veterans.¹⁹ This application addresses several CSR&D priority research areas (Pain Management, Complementary and Alternative Medicine, Patient-Centered Care) and coincides with a nationwide VHA/DoD initiative to include complementary, integrative, therapies into pain management for Veterans. To our knowledge, the use of HRV-B to improve chronic pain symptoms in a Veteran population has not previously been studied in a randomized clinical trial.

Chronic Pain, Stress, Depression and Autonomic Imbalance. HRV is a valid, noninvasive measure of autonomic function with both physiological and psychological attributes. Reduced HRV is an established risk factor for mortality due to cardiovascular or other chronic diseases.^{20,21} For example, about 80% of advanced

[figure not shown]

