1.1. Preliminary Studies

We are now conducting a randomized, single blind, sham-controlled study funded by the Department of Defense (DoD) to examine the effectiveness of HRV-B in alleviating PTSD symptoms. Three groups of combat veterans are being studied: (1) PTSD patients who received active HRV-B training (n=30); (2) PTSD patients who received sham HRV-B training (n=30); and (3) Veterans without PTSD who were assessed only at baseline and received no HRV-B training. Training lasted six weeks. Participants were assessed Pre-training, immediately Post-training, and 8 weeks after training. To date, 73 participants have been enrolled, with 32 assigned to the Sham group, 29 to the active Biofeedback group, and 12 to the Control group. Data analysis is ongoing and results are being prepared for submission for review for publication.

Effect of HRV-B on HRV Coherence. In this ongoing study, the time domain variable RMSSD was used as an

[figure not shown]

indicator of coherence because it correlates very highly with vagal tone and parasympathetic output ($r=0.853$, $p<0.001$).^{52,53} Linear mixed model analysis of RMSSD for Group (Sham vs. HRVB) x Time Period of Assessment (Pre-, Post-, Follow-up) showed that the interaction effect was significant, $F(5, 125)=2.50$, $p=.034$. Follow-up testing of the interaction effect revealed that the Group main effect was statistically significant, $HRV-B > Sham$, $60.2 (43.6)$ vs. $46.1 (37.3)$, $F(1,127)=4.66$, $p=.033$. Contrasts within the HRV-B group revealed that Pre-training RMSSD was statistically lower than combined Post-training and Follow-up, $44.1 (22.8)$ vs. $72.6 (51.4)$, $t(57)=-2.58$, $p=.013$, but Post-training was not

statistically different from Follow-up, $74.8 (63.2)$ vs. $69.7 (32.8)$, $t(57)=0.346$, $p=.730$. In summary, active HRV-B increased HRV coherence and the increase persisted until the Follow-up period (Figure 3).

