For each of the outcomes, there will be three measurements per subject (post-training minus pre-training, 4-week booster minus post-training, and 8-week follow-up minus the 4-week booster assessment). To test the effect of HRV-B relative to controls, we will apply linear mixed models for repeated measures data. Models will include the group (intervention or sham), time, and the interaction between group and time as the main independent variables. The effect of the intervention on the outcome could be non-linear in time, thus we will evaluate the inclusion of time as a nominal or ordinal variable and choose the specification that has the best fit in terms of the model assumptions and the BIC statistic. Covariates to be considered in the models include (but are not limited to: age, type and duration of usual pain treatment or medication, or other outcomes that may modify the effect (e.g., stress, pain, sleep). We will use a variable selection procedure to screen and identify all variables that differ among the treatment and control groups (initial selection set at $p < 0.15$), and we will include them in the final statistical model if their inclusion alters the effect estimate for HRV-B by $\geq 10\%$. Linear mixed effect models will be implemented using the PROC MIXED procedure in SAS (v9.3, SAS Institute). The conceptual model of each linear mixed model is:

$$Y_{ij} = \beta_0 + \beta_1 X_{ij} + \beta_2 t_j + \beta_3 X_{ij} \times t_j + s_i + \varepsilon_{ij},$$

where Y is the dependent variable, X is the independent variable of interest (or a vector of covariates), s_i is a subject-specific random effect, and t represents the outcome assessment time points (baseline, follow-up). The β coefficients measure each independent variable's effect. If time is included as an ordinal variable,

significance between treatment and control groups will be tested using Wald tests for appropriate β coefficients. If time is included as a nominal variable, we will use least squared means to test for significant differences between treatment and control groups at each of the post-intervention time points (post-training, booster, 8-week follow-up). In this situation we will use a Bonferroni adjusted alpha level = 0.005 (0.05/10), which results in at least 78% power for all of the outcomes with 25 per group to account for attrition (data not shown).

[figure not shown]

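### Treatment persistence is an analysis target, but the plan defines its measurements as adjacent-visit changes and names no contrast that tests benefit at 8 weeks

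*Combined protocol and SAP*

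**What the plan says.** The study summary at the front of the document names persistence as something the repeated-measures models will evaluate, and goes straight on to the change scores: "and on treatment persistence, after adjusting for confounding factors. For each measure we will calculate three estimates of change for each patient".

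Section 2.3 (Statistical Analyses) makes these the data for each outcome: "there will be three measurements per subject (post-training minus pre-training, 4-week booster minus post-training, and 8-week follow-up minus the 4-week booster assessment". The models then contain group, time and their interaction. If time is nominal, least-squares means are compared between the treatment and "control groups at each of the post-intervention time points (post-training, booster, 8-week follow-up", at a Bonferroni alpha of 0.005. Section 2.3 does not say whether that comparison is of outcome levels, changes from baseline, or the increments just defined.

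Section 1.0 adds that in the path analysis "we will identify factors predicting persistent HRV-B effects at the 8-week post-treatment follow-up". No section gives a persistence estimate, a retained fraction, a confidence-interval rule or a power figure for persistence. Table 3 covers only the pre-post change.

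The preliminary studies in section 1.1 reach persistence conclusions in two ways. For RMSSD in the PTSD study, post-training was not "statistically different from Follow-up, $74.8 (63.2)$ vs. $69.7 (32.8)$, $t(57)=0.346$, $p=.730", and the text concludes that "active HRV-B increased HRV coherence and the increase persisted until the Follow-up period". For CAPS, persistence is concluded alongside a significant pre to follow-up change.

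**The concern.** An adjacent-visit change answers a different question from persistence. If HRV-B beats sham after training and the advantage is fully kept, the arm difference in booster minus post-training is zero, and so is the difference in 8-week minus booster. A group comparison of the 8-week increment is then null when the treatment has done best. A significant result would mean a late gain or a late loss, not lasting benefit.

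There are two consequences. The question the 8-week visit is there to answer has no named test. And a gradual fade is cut into two smaller pieces, each tested separately at a strict alpha, so it is harder to see than it would be in one contrast. With no rule written down, whoever reports the trial must decide afterwards what a non-significant later change means.

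**Working it through.** **Inputs.** Table 3 arm difference D and SD: negative emotion 15.5 − 4.5 = 11, SD 10; activity limitation 14 − 4 = 10, SD 9.5; pain 10 − 1.8 = 8.2, SD 5; stress 4 − (−1.2) = 5.2, SD 4.5; coherence 0.17 in absolute value, SD 0.15. Sizes: 40 per arm planned, 25 per arm as the attrition case. Alpha 0.005 for the nominal-time comparisons.

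**The plan's own figures.** Two-sample t-test power from the noncentral t, df = 2n − 2, noncentrality D/(SD·√(2/n)). At alpha 0.01 this reproduces Table 3 (activity limitation 84.5% at 25 and 97.9% at 40); the only differences are the pain cells at 30 and 40, which compute to 100.0% and are printed as 99.9%. At alpha 0.005 and 25 per arm the lowest value is 77.7%, matching the stated 78%.

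**What each contrast tests.** Let the arm difference from baseline be D at post-training, B at booster and F at 8 weeks. The increments have arm differences D, B − D and F − B. Full persistence (D = B = F) gives D, 0, 0. The sum D + (B − D) + (F − B) = F is the 8-week arm difference from baseline. It can be recovered from the increments, but the plan does not name that sum as a contrast.

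**Cost of splitting a fade.** Assumptions: the whole of D is lost in two equal steps; the Table 3 SD applies to each change; visit variances are equal and visit errors independent. A change between any two visits then has the same SD, and adjacent changes correlate at −0.5 because they share the booster visit. The joint miss is simulated; the other columns use the noncentral t. All are at alpha 0.005, given as 25 / 40 per arm.

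| Outcome | Power for one step (D/2) | Missed at both steps | Missed by one 8-week minus post-training contrast |
|---|---|---|---|
| Negative emotion | 17% / 34% | 66% / 38% | 18% / 2.4% |
| Activity limitation | 15% / 30% | 70% / 43% | 22% / 3.8% |
| Pain | 49% / 78% | 19% / 1% | 0.3% / <0.1% |
| Stress | 20% / 39% | 61% / 31% | 13% / 1.3% |
| Coherence | 19% / 37% | 63% / 33% | 15% / 1.7% |

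Simulation runs differ by about one point. Hand check for activity limitation at 25 per arm: if the two tests were independent the joint miss would be (1 − 0.153)² = 72%; the negative correlation brings it to 70%.

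**Power of the baseline-anchored contrast.** Under the same assumptions the 8-week change from baseline has the Table 3 SD, so if benefit fully persists its power is that of the pre-post effect: at least 78% at 25 per arm and at least 96% at 40.

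**The preliminary RMSSD contrast.** Loss 74.8 − 69.7 = 5.1; SE = 5.1/0.346 = 14.7; 95% CI 5.1 ± 2.00 × 14.7, about −24 to +35. The gain was 74.8 − 44.1 = 30.7.

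**The case against.** **The plan may already compare arms at 8 weeks.** Section 2.0 says endpoints will be tested 8 weeks after training, and the model in section 2.3 indexes time by assessment points that include baseline. If the dependent variable is the outcome level, the nominal-time comparison does test benefit at 8 weeks. This stands as a possible reading, but section 2.3 defines the measurements per subject as increments and nowhere reconciles the two.

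**The increments are not uninformative.** They sum to the 8-week change from baseline, so it would be wrong to say that persistence can appear on this scale only as a null result. What is missing is the named contrast.

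**A reader might infer that the sponsor will treat a non-significant change as persistence.** The documents do not say so for this trial. The RMSSD conclusion comes from another study and also follows a significant contrast of pre-training with post-training and follow-up combined (44.1 vs 72.6, p=.013). The CAPS conclusion uses a significant pre to follow-up change.

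**A reader might also infer that the RMSSD gain could have been lost entirely.** The interval for the loss does reach 35, but it treats the gain of 30.7 as fixed. The direct comparison is follow-up with pre-training, 69.7 − 44.1 = 25.6. RMSSD group sizes are not printed. Assuming those of Table 1 (29, 16, 12), which reproduce the combined mean ((16 × 74.8 + 12 × 69.7)/28 = 72.6), a Welch interval is 3.6 to 47.6. Using the error term implied by t(57) gives −0.9 to 52. The point is borderline, not settled.

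**It would be too strong to say that the trial would usually miss a relevant fade.** At 40 per arm, complete loss in two steps is found more often than not for every outcome, and a half loss of the pain effect in one step is found 78% of the time at alpha 0.005. The documents do not define a relevant fade.

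**Conclusion.** The concern holds in a limited form. Persistence is a stated target, the measurements are defined as adjacent-visit changes, and no contrast for benefit at 8 weeks is named. Read literally, the later group comparisons test increments that are zero when benefit lasts.

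The loss from splitting a fade is material. For complete loss in two equal steps at alpha 0.005, the joint miss is about 61–70% at 25 per arm for four outcomes (19% for pain) and 31–44% at 40 (1% for pain), against 0.3–22% and under 4% for one contrast. These figures rest on Table 3 SDs for the later changes, equal visit variances and independent visit errors, none of which the documents state. Smaller SDs for the later changes would lower the miss rates and larger ones would raise them.

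The documents do not support saying that this plan equates non-significance with persistence, or that a fade would usually be missed at the planned size. The defect is an unspecified persistence estimate combined with an unsuitable choice of change scores.

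**What to change.** In the study summary and in section 2.3:

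- Define the persistence estimate as the HRV-B minus sham difference in change from baseline at 8 weeks, tested at the planned alpha and reported with its confidence interval.
- Report the loss, meaning the arm difference in 8-week minus post-training, with its confidence interval.
- State whether the dependent variable in the mixed model is the level, the change from baseline or the increment.
- State that a non-significant adjacent-visit change is not evidence of persistence. The adjacent changes can stay as description.

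This changes wording only and needs no new data or visits. The downside is that a claim that benefit was maintained becomes slightly harder to support.

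Two additions are optional. One is a pre-set margin for calling benefit maintained, for example loss of no more than half the post-training effect. With no true fade, one-sided 0.025, 80% power and Table 3 SDs, that needs 52, 57, 24, 48 and 49 per arm (negative emotion, activity limitation, pain, stress, coherence), so 40 per arm reaches it only for pain. The other is to give the confidence interval beside the RMSSD conclusion in section 1.1.

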
1.0 BACKGROUND AND SIGNIFICANCE

Pain is the most common reason for seeking health care in the United States, impacting ~116 million Americans and generating >\$600 billion in medical care costs.¹ Chronic pain is a significant issue among Veteran patients and is one of the most common reasons for seeking care among Veterans of all wars.^{2,3} Among all Veterans, musculoskeletal pain is the most commonly diagnosed medical problem.⁴ Pain patients experience improved quality of life when pain is controlled and they are more likely to successfully manage other aspects of their daily lives.⁵ Because the prevalence and intensity of pain increases with disease progression, and since pain impacts multiple domains of quality of life (QoL),^{6,7} the ability to manage pain becomes increasingly important over time for medical patients of all types.

Pain initiates a stress response that increases sympathetic output leading to autonomic imbalance and psychological stress; physical and psychological stress in turn exacerbates pain, thus creating a self-perpetuating cycle of autonomic dysregulation that facilitates persistent pain.⁸ Stress from chronic pain leads to loss of the glucocorticoid (GC)-mediated negative feedback control of the hypothalamic-pituitary-adrenal (HPA) axis, producing positive HPA drive and down-regulation of central and peripheral GC receptors. In addition, peripheral cytokine pro-inflammatory signals from nociceptive receptor chronic stimulation is sent to the spinal dorsal horn and ascends to brainstem, and gated in thalamus prior to cognitive appraisal in primary somatosensory cortex. This creates pain awareness. As a result, monoaminergic (dopamine, norepinephrine and epinephrine) neurons in the brainstem that normally descend to the spinal cord and 'brake' nociceptive transmission become depleted during chronic pain.⁹ This loss of inhibitory monoaminergic tone to the spinal cord leads to enhancement of pain ('central sensitization'). In what is now a feed-forward system, the loss of GC inhibition of pro-inflammatory cytokines leads to proliferation of peripheral inflammatory agents, which are nociceptive transmitters, further contributing to central pain sensitization and an HPA driven stress response.¹⁰ At the same time, down-regulation of GC negative-feedback modulation from chronic stress also promotes depressed mood.¹¹ Thus, chronic pain can induce both stress and depression (Figure 1, 'Disease Pathway').

[figure not shown]
Pain Medication & Addiction. Pain remains a major healthcare problem despite advances in treatment of major medical illnesses and illness-related pharmacological pain management.¹² Opioid analgesics such as morphine and hydrocodone and its derivatives effectively produce analgesia through antagonism of the receptors of naturally occurring opioids that are released from the periaqueductal gray region of the central nervous system in response to pain. However, the use of opioid analgesic medication poses an increased risk of physical and psychological addiction, as well as a number of other side effects including intolerance, hyperalgesia, hormonal imbalance, respiratory depression, constipation, nausea, vomiting, drowsiness, and itching.¹³ Nonetheless, Vicodin is the most prescribed medication in the United States.¹⁴ Overdose deaths from opioid painkillers have more than quadrupled since the turn of the century, approaching 20,000 annually, and opioid overdose is the leading cause of accidental death in several states.¹⁵ Many Veterans with mental health diagnoses receive prescription opioids for pain-related conditions, which can compromise their mental health.¹⁶ An effective non-pharmacological pain therapy that reduces the usage of opioid medications would be a significant benefit to chronic pain patients.

Non-Pharmacological Pain Treatment. Many veterans in chronic pain use avoidance strategies to dampen the intensity of pain in their lives. This avoidance is most clearly seen in behaviors and movement. Painful activities are avoided in an attempt to decrease the overall experience of pain. Though behavioral avoidance can lessen pain in the short term, it can also cause long term problems and decrease QoL.¹⁷ Complementary therapies, such as Heart Rate Variability (HRV) Biofeedback (HRV-B), that can help improve both physical and psychological well-being have been advocated for integration with conventional therapies because many medical patients are not satisfied with mainstream treatments in relieving their pain symptoms and the attendant erosion of their QoL.¹⁸

Our proposal is designed to test whether HRV-B is feasible and effective in increasing HRV coherence and reducing perceived pain, stress, depression, and insomnia among Veterans suffering from chronic physical pain. Our path analyses will examine both direct and indirect relationships between HRV-B, the primary and exploratory outcomes, and other individual or social factors that may modify this relationship. The relationship

between autonomic dysfunction and disrupted sleep has not been thoroughly examined. Our path analyses are thus important from a practical standpoint because HRV coherence and sleep represent potentially modifiable risk factors that can be targeted to reduce symptom burdens and improve QoL for Veteran patients. In addition, we will implement the use of portable, hand held finger plethysmographs (personal stress relievers) to reinforce the HRV-B training and promote practice outside the clinic. We have obtained encouraging preliminary results by incorporating this technique in our other research. In our path analysis, we will identify factors predicting persistent HRV-B effects at the 8-week post-treatment follow-up. This information will be useful in designing future interventions. The use of HRV-B to normalize autonomic function represents a novel, complementary strategy that engages patients in their own care and is directly responsive to the VHA/DoD Pain Management Task Force’s recommendations to adopt complementary pain management strategies (including HRV-B) to alleviate pain among Veterans.¹⁹ This application addresses several CSR&D priority research areas (Pain Management, Complementary and Alternative Medicine, Patient-Centered Care) and coincides with a nationwide VHA/DoD initiative to include complementary, integrative, therapies into pain management for Veterans. To our knowledge, the use of HRV-B to improve chronic pain symptoms in a Veteran population has not previously been studied in a randomized clinical trial.

Chronic Pain, Stress, Depression and Autonomic Imbalance. HRV is a valid, noninvasive measure of autonomic function with both physiological and psychological attributes. Reduced HRV is an established risk factor for mortality due to cardiovascular or other chronic diseases.^{20,21} For example, about 80% of advanced

[figure not shown]
cancer patients exhibit autonomic dysregulation,^{20,22} and several recent studies report increased mortality risk among patients with reduced HRV.²⁰⁻²⁶ Furthermore, emotional disruption caused by a stressful experience is characterized by a chaotic, disordered pattern of inter-beat intervals as well as an increased heart rate, which lowers HRV (Figure 2, top panel). Irregular heart beat rhythm due to disordered inter-beat intervals, reflects sympathetic nervous system over-activity and low HRV coherence. In contrast, emotional balance and a feeling of well-being results in an ordered, sine wave-like pattern of inter-beat interval changes and a narrow peak in the low frequency (LF) range of the power spectrum, centered around 0.1 Hz, which equals a period of 10 seconds, or 6 cycles per minute (Figure 2, bottom panel).²⁷

As a measure of the interplay between the excitatory sympathetic and the inhibitory parasympathetic nervous systems, HRV has a clear relationship with pain sensitivity and perception. Linkages between HRV alterations and various types of pain have been documented. Appelhans and Luecken found an inverse relationship between HRV and sensitivity to cold thermal pain measured as ‘unpleasantness’, and ‘threshold for barely noticeable pain’.²⁸ In patients with fibromyalgia, HRV was a predictor of pain perception, pain anxiety, and physical health functioning.²⁹ The pattern of HRV in patients under general anesthesia changed to reflect decreased vagal tone when a surgical stimulation was painful, even though the patient was not conscious.³⁰ Alternatively, a reduction in visceral pain during esophageal balloon distension was associated with higher HRV.³¹

The autonomic nervous system exhibits a distinct circadian rhythm as do several cardiac measures including heart rate and blood pressure.¹³ The heart rate increases in the morning at or after waking, reaches peak between 10 am to 12 pm, and then gradually begins to decline later in the day, maintaining a low level during night. During sleep, increases in parasympathetic tone and HRV predominate. Despite these associations, few

studies have examined relationships between disrupted sleep and autonomic function.^{16,32} In a study of 13 healthy male volunteers randomized to 5 nights of partial sleep deprivation (<5 h), or 5 nights of control sleep (>7 h), those with sleep deprivation had a statistically significant increase in sympathetic activity as indicated by an increase in low frequency (LF) and decrease in high frequency (HF) components of HRV.³³ The results were consistent with another study that reported increased sympathetic and decreased parasympathetic HRV measures after 36-hours of total sleep deprivation.³²

Depression is relatively common in patients with coronary heart disease (CHD) and its association with autonomic nervous system dysfunction has been investigated among CHD patients. HRV is lower among depressed patients with either stable CHD, or among those with a recent acute coronary event, compared with non-depressed patients.³⁴ Studies examining HRV and depression have expanded into other patient populations. Another recent meta-analysis concluded that depression in the absence of cardiovascular disease is also associated with reduced HRV, and that HRV decreases with increasing depression severity.³⁵ Reduced HRV is an established predictor of increased mortality risk both in cardiovascular or other chronic disease patients, and in the general population.^{20,21}

Loss of HRV coherence is also associated with PTSD. Our recently published meta-analysis of HRV and PTSD found that HRV variables are associated with PTSD, and these associations can be interpreted in terms of a basic and widespread model of PTSD as a disorder comprising hyper-arousal of the sympathetic nervous system (see Preliminary Studies).³⁶

HRV Biofeedback. Improvements in HRV can be therapeutic. Complementary therapies, such as HRV-B that can help improve both physical and psychological well-being have been advocated for integration with conventional therapies. HRV-B is an interactive procedure whereby patients increase HRV in real time by practicing focused attention, positive emotion, and resonant frequency

breathing. Previous research suggests that HRV-B interventions may be useful for reducing symptoms of: chronic pain,^{28,31,37,38} anxiety,³⁹⁻⁴¹ depression,^{37,42} post-traumatic stress disorder (PTSD),^{43,44} heart disease,⁴⁵ and insomnia.⁴⁶

HRV-B is a complementary, non-pharmacological technique for improvement of HRV and autonomic function. It is an interactive procedure whereby patients monitor their HRV patterns in real time while practicing focused attention, positive emotion, and resonant frequency breathing. The resonant frequency of breathing (RFB) is the respiratory rate producing the highest HRV in the LF band; RFB is necessary for attainment of HRV coherence.⁴⁷ HRV coherence is achieved when beat-to-beat intervals increase and decrease in a smooth rhythm, producing a spike around a 10 second period (0.1 Hz on the fast Fourier transformation to the power spectrum) of the instantaneous heart rate (Figure 2). It is defined according to consensus guidelines as the ratio of power in the LF peak to the remainder of power in the HRV spectrum.^{27,44,48} Using HRV-B, patients learn how to produce HRV patterns indicative of higher vagal parasympathetic tone. With practice, patients acquire the ability to enhance their HRV coherence on demand (see Figure 2). High coherence has been associated with a favorable psychological state, including improved affect, cognition, and executive function.²⁷

HRV-B had analgesic effects on experimental heat pain threshold and tolerance scores in normal subjects.⁴⁹ The HRV-B technique has been used in several clinical settings to improve HRV and reduce pain symptoms of fibromyalgia,³⁷ back pain,³⁸ and chronic stress-related neck pain.⁴¹ In our own work⁵⁰ with chronic pain patients from our DVAMC Pain Clinic, several pain and stress perception ratings were lowered by HRV-B compared to

[figure not shown]
a control group of treatment as usual. Thus, the neurobiology underlying analgesia induced by this method of complementary, non-pharmacological, psychophysiological self-regulation appears to be different from other commonly used techniques involving distraction. The potential benefits of improving autonomic function among medical patients has been acknowledged.^{20,21,26,51}

Chronic pain is a significant issue among Veterans, and to our knowledge, this will be the only study other than our pilot study⁵⁰ to evaluate HRV-B for the amelioration of pain in this population. The alleviation of persistent pain, fatigue, insomnia or depression via improved HRV coherence may provide a direct clinical benefit to Veteran pain patients. Our study will examine both direct and indirect relationships between HRV-B, the primary and exploratory outcomes, and other individual or social factors that may modify this relationship. We will also develop an integrated statistical model of autonomic dysfunction as a potential underlying psychophysiological process that can be targeted to improve the management of pain. This will include the identification of predictors of disrupted sleep and rest/activity rhythms. If our aims are achieved, our study has importance from a practical standpoint because HRV coherence and sleep represent potentially modifiable risk factors that can be targeted to reduce symptom burdens and improve QoL for pain patients. The integrated path analysis model derived from this study will aid in the development of more effective intervention strategies for addressing symptoms and thus targets for the design of future projects. If this study's hypotheses are supported, we will seek funding for a full-scale intervention to comprehensively examine whether HRV-B therapy alleviates pain in a wider population of Veterans with pain.

